Recruitment occurred and written informed consent was obtained during regularly scheduled preoperative office visits. If no preoperative visit was scheduled, informed consent was performed by telephone and the consent form was either mailed to the patient or signed on the morning of surgery. Block randomization occurred 1-2 days prior to scheduled surgery in a 1:1:1 ratio by a research coordinator not involved in study intervention or outcome assessment. The randomization scheme was stored in a password protected, secure location and only accessed by this research coordinator. We also took additional steps to ensure a double-blinded design. After randomization but before the start of the prolapse procedure, pharmacy personnel delivered the study medication to the operating room in a single, clear syringe labeled "Study Medication" and the corresponding study identification number. All syringes were identical. Additionally, normal saline, bupivacaine and dexamethasone are all clear solutions, which allowed us to blind physicians to the study medication being administered. Patients were also blinded to the study intervention until 12 weeks of follow-up.

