To standardize care, all study participants received the same institutional induction and intraoperative enhanced recovery after surgery general anesthesia protocol, full details of which have been previously published (23). In summary, patients received intravenous propofol, ketamine, lidocaine, muscle relaxant and dexamethasone for induction and intravenous ketamine and lidocaine for maintenance (23). The intravenous dexamethasone given upon induction is part of the protocol to prevent postoperative nausea and vomiting. To standardize intraoperative local anesthetic, the amount of additional local infiltration was limited to 50ml of 0.5% lidocaine with epinephrine. According to our ERAS protocol, all surgeries were planned to be same-day surgeries. Any deviations from protocol were documented.

Our primary outcome was a numeric rating scale (NRS) pain score on postoperative day (POD) one. The NRS is an eleven-point scale ranging from 0 to 10 presented visually on a horizontal line. Higher scores represent more postoperative pain.

Secondary outcomes included pain scores at additional timepoints (6 hours after surgery, POD 2, POD 3 and 1 week after surgery), same day discharge rates, voiding status at time of discharge, postoperative narcotic consumption measured in oral morphine equivalents, postoperative ibuprofen consumption, postoperative nausea and vomiting (PONV), postoperative activities assessment, and adverse events. PONV was assessed using the PONV Intensity scale, a four-question assessment to measure clinically significant nausea and vomiting with higher scores signifying more clinically significant PONV (26). Time to resume normal activities was measured by the activities assessment scale (AAS), a 13-point scale on which patients rate their difficulty performing a range of activities from "No difficulty" to "Not able to do it." A final score ranging from 0-100 is transformed, with higher numbers reflecting less difficulty with activities (27). Assessments were completed by the patient at home and mailed to research staff upon completion. Women were followed for 12 weeks postoperatively and no additional office visits were required as part of the research protocol.

Eligibility Criteria

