Women were eligible for inclusion if they were ≥18 years old and scheduled for a vaginal native tissue repair with apical support procedure (uterosacral ligament suspension, sacrospinous ligament fixation, levator myorrhaphy or colpocleisis) and able to undergo general anesthesia. Concomitant procedures including hysterectomy, anterior and posterior colporrhaphies, perineorrhaphies and midurethral sling placements were permitted. All patients needed to be available for at least 12 weeks of follow-up. Women were excluded for any of the following reasons: planned mesh-augmented apical support procedure or mesh excision, laparoscopic, robotic or abdominal surgery, known adverse reaction or allergy to intervention medication, evidence of fistula or infection, chronic pelvic pain as an active issue, daily opiate

consumption, history of pelvic radiation, daily steroid use, diabetes mellitus, immunosuppression, planned surgery under regional anesthesia, non-English speaking or inability to complete questionnaires, bleeding diatheses, or weight less than 50kg. We incorporated a weight less than 50kg as an exclusion criterion to ensure that the bupivacaine dosage was below the weight-based maximum dose, as recommended by our anesthesia colleagues (16).

Statistical Analysis Plan

All results will be analyzed by intention-to-treat based upon the study group to which subjects were randomized. One-way ANOVA, Kruskal Wallis, Chi-square, and Fisher's Exact will be used to compare continuous and categorical variables, respectively. Based upon prior studies demonstrating that pain after vaginal surgery ranges from a 2 to 5 on numeric scales (range 0-10) and literature suggesting that a 33% decrease in pain is clinically significant, we elected to assess a 2-point change in NRS scores between treatment groups (5,7,9,28). Based upon an ANOVA evaluated at the 2-sided 0.05 significance level and a standard deviation of 17.5, a sample size of 21 patients per arm provided 90% power to detect a 2-point change in NRS scores. To account for 20% attrition, we increased to 25 patients per arm for a total of 75 women.

We hypothesized that concurrent bilateral transobturator levator ani muscle injections and transvaginal pudendal nerve blocks with bupivacaine and dexamethasone performed prior to vaginal native tissue apical prolapse repair would result in statistically significant improved pain scores on postoperative day one.

References

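### Twenty-five per arm does not cover 20% attrition: it leaves 20 per arm, one short of the 21 behind the stated 90% power, and covers at most 16% loss

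*Combined protocol and SAP*

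**What the plan says.** The sample-size paragraph of the Statistical Analysis Plan bases the calculation on a one-way ANOVA and a 2-point difference on the numeric rating scale (NRS), and reports that "a sample size of 21 patients per arm provided 90% power to detect a 2-point change in NRS scores". The next sentence enlarges that number: "To account for 20% attrition, we increased to 25 patients per arm for a total of 75 women". It gives no inflation formula, no second attrition rate and no time point to which the 20% refers.

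The same section sets the analysis principle: "All results will be analyzed by intention-to-treat based upon the study group to which subjects were randomized". It names no method for a missing primary score. Under Study Design & Methods, allocation is 1:1:1 to three arms, and patients complete the assessments at home and mail them back.

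**The concern.** An attrition allowance is meant to leave the planned evaluable number after the planned loss. Here the planned loss, applied to the planned enrolment, leaves fewer patients than the number to which the plan attaches 90% power. The intention-to-treat statement does not close the gap: without a method for missing scores, a patient with no day 1 score adds nothing to the primary comparison.

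What is at stake is mainly how the trial is read. Someone using the paragraph to judge whether losses stayed within the design would accept anything up to 20%. Above 16%, fewer than 21 per arm remain.

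**Working it through.** **Inputs, all from the Statistical Analysis Plan:** 21 per arm for 90% power; 20% attrition; 25 per arm enrolled, 75 in total. The three equal arms come from Study Design & Methods.

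**Where 25 may come from.** Adding 20% to the base gives 21 × 1.2 = 25.2, which rounds down to 25. The plan does not show its formula, so this is an inference. Rounded up, as is usual for a sample size, even that formula gives 26.

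**What 25 delivers at 20% loss.** 25 × (1 − 0.20) = 20 per arm, and 75 × 0.80 = 60 in total, against 21 per arm and 3 × 21 = 63 in total. The shortfall is one per arm, three overall.

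**What loss 25 can absorb.** 1 − 21/25 = 4/25 = 16%.

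**What a 20% allowance would take.** n/(1 − d) = 21/0.80 = 26.25, so 27 per arm and 81 in total. Check: 26 × 0.80 = 20.8, too few; 27 × 0.80 = 21.6, enough. Inflating the total instead gives 63/0.80 = 78.75, so 79, which becomes 81 with equal arms.

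**Effect on power.** The test is a one-way ANOVA with 3 arms and level 0.05. Power comes from the noncentral F distribution with 2 and 3(n − 1) degrees of freedom and noncentrality n × Σ(mean − grand mean)²/SD². The plan gives neither a usable SD nor the three means, so the inputs below are assumptions, apart from the printed SD of 17.5. The SD of 1.75 is used because, with means 0/1/2, 21 is then the smallest number per arm that reaches 90%; the documents do not state it.

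| SD | Means | Noncentrality at n = 21 | Power, n = 20 | Power, n = 21 | Power, n = 25 | Power, n = 27 |
|---|---|---|---|---|---|---|
| 1.75 | 0/1/2 | 21 × 2/3.0625 = 13.7 | 89.3% | 90.9% | 95.3% | 96.6% |
| 1.75 | 0/0/2 | 21 × 2.667/3.0625 = 18.3 | 96.2% | 97.0% | 98.8% | 99.3% |
| 17.5 | 0/1/2 | 21 × 2/306.25 = 0.14 | 5.9% | 6.0% | 6.2% | 6.3% |
| 17.5 | 0/0/2 | 21 × 2.667/306.25 = 0.18 | 6.3% | 6.3% | 6.6% | 6.7% |

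With SD 1.75, moving from 21 to 20 per arm costs 90.9 − 89.3 = 1.6 points under means 0/1/2 and 97.0 − 96.2 = 0.8 points under means 0/0/2. Only the first pattern falls below 90%.

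**Why the printed SD cannot be used.** The paragraph reads "a standard deviation of 17.5, a sample size of 21 patients per arm provided 90% power", while Study Design & Methods states that "The NRS is an eleven-point scale ranging from 0 to 10". On that range the SD is largest when half the scores are 0 and half are 10. It is then 5.0 in a population and about 5.1 in a sample of 21.

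**The case against.** The strongest reply is about weight. The plan says that 21 per arm gave 90% power; it does not call 21 a minimum. With SD 1.75 and means 0/0/2, 90% is already reached at 16 per arm, so 20 would be ample. With the printed SD, power is about 6% at 20, 21, 25 or 27 per arm, and one patient per arm changes nothing. The SD is plainly the larger defect in the paragraph, and correcting it could change the 21 itself. The four extra patients per arm are also a real allowance, worth 16%. Finally, the 20% has no time point: if it means loss over the 12 weeks of follow-up, fewer day 1 scores might be missing.

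Most of this stands, and it limits the point to a minor one. It does not remove the inconsistency. The plan presents 25 as 21 enlarged for 20% loss, and on its own figures it is not. Correcting the SD while leaving 21 and 25 as printed would leave the attrition sentence wrong. The time-point argument is possible, but the plan does not make it, and because the assessments were mailed back, day 1 scores can be lost too. Reading the 20% as an addition to the base does not rescue 25 either, since 25.2 rounds up to 26.

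**Conclusion.** The point holds. It is a minor arithmetic error, established with high confidence from two adjacent sentences: the tolerance is 16% where the plan claims 20%. This takes 21 as the plan states it and does not depend on how 21 was derived. It also assumes that attrition means the share of enrolled patients without an evaluable primary score.

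The consequence for power is not established. On the assumed SD of 1.75 it is a loss of 0.8 to 1.6 points, and whether 90% is still met turns on a pattern of means that the plan does not give.

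**What to change.** Keep 75 women and replace the attrition sentence with one that matches the numbers, for example: *Twenty-five patients per arm (75 in total) retain 21 evaluable per arm at up to 16% attrition; at 20% attrition, 20 per arm remain.*

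The sponsor should confirm the SD and state the three assumed means. If that changes the 21, the percentages in the new sentence must be recalculated from the new number. Only then should a power figure for 20 per arm be added. It would also help to say whether the attrition rate refers to the day 1 score or to the full 12 weeks.

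The cost is one corrected sentence, with no added enrolment and no change to the analysis. The drawback is that the declared attrition tolerance falls from 20% to 16%. Keeping the 20% claim instead would mean 27 per arm, which is 81 − 75 = 6 more women; an effect this small does not call for that.

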Our primary aim is to determine if bilateral transobturator levator ani muscle injections and transvaginal pudendal nerve blocks with bupivacaine and dexamethasone improve postoperative pain measured by the numerical rating scale (NRS) on postoperative day 1 after vaginal reconstructive apical support procedures.

Our secondary aims include postoperative nausea and vomiting (measured by the postoperative nausea and vomiting score), analgesic consumption (measured in morphine equivalents), same-day discharge, postoperative pain at 6 hours, 48 hours, 72 hours and 1 week (measured by the NRS), need for either self-catheterization or indwelling catheter, safety and adverse events, and time to resume normal activity (measured by the activities assessment scale at 1,2,6 and 12 weeks postoperatively).

Study Design & Methods

We performed a 3-arm, double-blind, randomized, placebo-controlled trial of bilateral transobturator levator ani muscle injections and transvaginal pudendal nerve blocks

prior to native tissue vaginal apical support procedures for pelvic organ prolapse. Women were randomized to one of three study medication groups distributed over 4 injection sites: 22mL of 0.9% saline (placebo group), 22 mL of 0.25% bupivacaine (bupivacaine group), or 20 mL of 0.25% bupivacaine with 4mg (2mL) of dexamethasone (combined group).

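### The hypothesis is about the combined arm, but POD 1 pain is to be analysed and sized on a three-arm omnibus test, with no deciding comparison or effect estimate named

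*Combined protocol and SAP*

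**What the plan says.** The primary aim (Study Objectives) is to find out whether injections "with bupivacaine and dexamethasone improve postoperative pain measured by the numerical rating scale (NRS) on postoperative day 1". The hypothesis at the end of the Statistical Analysis Plan predicts that the same combination "would result in statistically significant improved pain scores on postoperative day one". Both concern one arm and one direction. Neither says better than which arm.

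The Statistical Analysis Plan lists its tests in one sentence. "One-way ANOVA, Kruskal Wallis, Chi-square" and Fisher's exact test "will be used to compare continuous and categorical variables, respectively". The sample size is "Based upon an ANOVA evaluated at the 2-sided 0.05 significance level", and for the target "we elected to assess a 2-point change in NRS scores between treatment groups". No pair of groups is named.

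Study Design & Methods describes a placebo-controlled trial of saline, bupivacaine alone, and bupivacaine with dexamethasone, and labels the saline arm as placebo. Scientific Background refers to the combined arm as the intervention group. The role of the bupivacaine-alone arm is not defined. No section gives a contrast, a pairwise procedure, a testing order, or a between-arm difference with a confidence interval.

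**The concern.** With three arms, one-way ANOVA and Kruskal-Wallis test whether the arms are all alike. A significant result does not say which arm differs or in which direction, so on its own it neither confirms nor refutes a claim about the combined arm. The comparison that decides the matter would have to be chosen later. An F or H statistic also gives nothing to set against the 2-point target that the plan calls clinically relevant.

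Three things are at stake: how often a significant omnibus result would support the stated hypothesis, how much power is lost by going through the omnibus test, and whether the reader gets an estimate of benefit.

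**Working it through.** **Inputs.** From the Statistical Analysis Plan: three arms, 21 per arm, two-sided 0.05, a 2-point difference, ANOVA. The SD is an assumption: 1.75, with a range of 1.5 to 2.5. The documents do not give these values. Means are changes from placebo in the order placebo, bupivacaine, combined, and each pattern is an assumption.

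**The plan's own figure.** The plan states "a standard deviation of 17.5, a sample size of 21 patients per arm provided 90% power". ANOVA power comes from the noncentral F distribution with 2 and 60 df (critical value 3.15) and λ = n Σ(μᵢ − μ̄)² / SD².
- SD 17.5, means (0,−1,−2): λ = 21 × 2 / 306.25 = 0.137, power 6.0%. With (0,0,−2), power is 6.3%. The printed SD does not reproduce the figure; that is a separate error.
- SD 1.75, (0,−1,−2): λ = 42 / 3.0625 = 13.71, power 90.9%. At 20 per arm it is 89.3%, so 21 is the smallest n.
- SD 2.0, (0,0,−2): λ = 56 / 4 = 14.0, power 91.5%. At 20 per arm it is just under 90%, so 21 is again the smallest n.

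The sizing fits an omnibus test under more than one pattern, so it does not reveal which pair was meant.

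**Direct contrast, combined v placebo.** With the pooled variance (60 df), SE = SD √(2/21). At SD 1.75, SE = 1.75 × 0.3086 = 0.540 and the noncentrality is 2 / 0.540 = 3.70, so power is 95.4%. The 95% CI half-width is 2.00 × 0.540 = 1.08 points.

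**Agreement.** In 1,000,000 simulated trials per case, agreement is the share of trials with a significant ANOVA in which combined is also significantly better than placebo. Power through the ANOVA is omnibus power times agreement: at SD 1.75, 0.909 × 0.997 = 0.906 for (0,−1,−2) and 0.970 × 0.973 = 0.944 for (0,−2,−2).

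| SD | Direct contrast | ANOVA first, (0,−1,−2) | ANOVA first, (0,−2,−2) | Agreement (0,−1,−2) | Agreement (0,−2,−2) | Agreement (0,−2,−1) | CI half-width |
|---|---|---|---|---|---|---|---|
| 1.5 | 98.9% | 97.2% | 98.7% | 99.9% | 99.2% | 58.1% | 0.93 |
| 1.75 | 95.4% | 90.6% | 94.4% | 99.7% | 97.3% | 48.6% | 1.08 |
| 2.0 | 89.0% | about 81% | about 86% | 99.2% | 94.5% | 42.8% | 1.23 |
| 2.5 | 72.3% | about 60% | about 66% | 97.7% | 88.8% | 37.5% | 1.54 |

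In the extreme pattern (0,−2,0), where the combination has no benefit, the ANOVA at SD 1.75 is significant in 97.0% of trials and combined beats placebo in 2.5%.

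**The other listed test.** Kruskal-Wallis on scores rounded and clipped to 0–10 (assumed placebo mean 5, SD 1.75, 20,000 trials) gives agreement of 99.6%, 97.4% and 49.5% for the three patterns in the table, so the choice between the two tests changes little.

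**The case against.** The strongest reply has four parts.

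First, placebo is the ordinary comparator in a placebo-controlled trial, and under the orderings that the rationale expects the omnibus result and the hypothesis nearly always agree. This stands. A reader might infer that the plan does not test its hypothesis at all. Agreement of 97.3% to 99.7% at SD 1.75 does not support that; the test is indirect, not absent.

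Second, a reader might infer that the intended claim is the gain from adding dexamethasone to bupivacaine. If so, under (0,−2,−2) combined would beat bupivacaine alone in only 2.5% of trials. But neither the aim nor the hypothesis makes that comparison, so this figure is no measure of failure against the stated hypothesis.

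Third, the poor agreement figures need the combined arm to do worse than bupivacaine alone. Dexamethasone was added because benefit was expected, so those patterns run against the rationale. They remain possible, which is the reason not to rely on an omnibus result alone.

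Fourth, the plan assigns no specific test to POD 1 NRS, and silence on follow-on comparisons is not a plan to exclude them. Pairwise tests after a significant ANOVA would hold familywise error at 5% with three arms. A reader might infer an inflated error of about 12%, but that arises only if all three pairs are tested without a gate or adjustment, which no section plans. What stands of the concern is that both candidate tests are omnibus, no follow-on step is written, and gating costs power for the one comparison that matters.

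**Conclusion.** The point holds in a moderate form and should be fixed. The plan states a hypothesis about one arm and addresses it through tests that name no arm, comparator or direction. If placebo is the comparator and the combined arm does at least as well as bupivacaine alone, the loss is the missing effect estimate plus, if a significant ANOVA is required first, 1.0 to 4.8 percentage points of power at SD 1.75 (95.4 − 94.4 and 95.4 − 90.6). At SD 2.5 the loss is about 6 to 12 points. If the combined arm does worse than bupivacaine alone, agreement falls to about half or lower, for example 48.6% under (0,−2,−1).

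The textual finding needs no assumption. The sizes rest on normal theory, 21 evaluable patients per arm, assumed mean patterns, and an SD that the documents do not give.

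**What to change.** Name one primary analysis: combined minus placebo in mean POD 1 NRS, estimated from the three-arm linear model with pooled variance, with a 95% CI and a two-sided test at 0.05. The sponsor should confirm that placebo is the intended comparator. The interval would be about ±1.1 points at SD 1.75 (0.9 to 1.5 for SD 1.5 to 2.5), which can be read directly against the 2-point target. Report the other two pairwise differences with CIs as secondary, state the role of the bupivacaine-alone arm, and keep ANOVA and Kruskal-Wallis as supportive.

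A fixed sequence that puts combined v bupivacaine ahead of bupivacaine v placebo should be avoided. Under (0,−2,−2) at SD 1.75 it would confirm a true 2-point bupivacaine benefit in only about 3.8% of trials, because the step before it has no true difference to find.

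The change needs no new data and no more patients. Its cost is that only one comparison is confirmatory. The secondary comparisons are also weak: power for a 1-point difference between combined and bupivacaine is about 45% at SD 1.75 (57% at SD 1.5, 25% at SD 2.5). Study Design & Methods is written in the past tense while the analysis is still in the future tense. If outcomes have already been seen by arm, new wording cannot restore pre-specification, and the contrast must be labelled as specified afterwards.
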